A subject will not be considered eligible unless all inclusion/exclusion criteria are met. Inclusion/exclusion criteria checklist will be signed at screen or baseline by both research coordinator and study physician.

For BAI, NYU, and NYSPI subjects, HSV antibody results take 2-4 days to be posted online in the e- portal, Quanum/Care 360; so results are not immediately known. Once the initial results are published, the RC will print them for the subject's chart and get signed by the study physician. Note: If the IgM results are "pending" from the results, the RC will continually monitor until the final results are published in Quanum/Care 360 to be printed and signed by the study physician.

To access results in Quanum/Care 360: https://portal.care360.com/care360/care360.login Username: [name] Password: [name]

Information concerning eligibility should be promptly communicated to the patient by the RC; for subjects who screen HSV negative, a study physician will have to reach out and inform of not only ineligibility but appropriate follow up.

Documentation of communication (via progress note filled out by study physician) of screen failed subjects must be kept in each screen failure chart at all study sites. All of this information needs to be presented in the team Wednesday morning meeting for all active patients, and any questions should be raised with the team, e.g., referral for specific ineligible patients.

Scheduling Baseline Measures: Procedures for NYSPI and NYU (BAI will follow this protocol with modification made per their site standard)

All baseline measures (PET scans, optional LP, MRI) should be scheduled once HSV positivity has been confirmed for those patients with qualifying MMSEs. It is important that all key measures get on the books as soon as possible to avoid unnecessary back and forth with patients or caregivers and to simply move the protocol along in an expeditious manner. Note, we must confirm at screen that patients and caregivers are available to come in on either a Monday or Friday for their Tau PET (18F-MK-6240 tau ligand exclusively available M/F). If the caregiver is not available, study staff will offer to arrange dropping off and picking up the patient (from tau PET) and do what we can to make it work. This is applicable to NYSPI/CU and NYU, BAI will schedule per their site standard.

Priority must be given to scheduling the MRI. Once the MRI has been confirmed, the PET scans and LP can be officially scheduled to accommodate the MRI.

If the patient would like to complete multiple procedures on the same day, schedule the MRI followed by amyloid PET on baseline day 1. An alternative is MRI followed by LP on baseline day 1. LP should be the last procedure for day 1. Theoretically, MRI followed by amyloid PET; followed by LP could be scheduled on the same day but this should be reserved for a highly cooperative and cognitively intact patient, with a sufficient gap of at least 2 hours between procedures to account for unanticipated delays for each procedure. The patient would still need to return a second day to complete the tau PET, which must be separated by at least 24 hours from the amyloid PET scan. When scheduling a PET scan and the LP on the same day: a gap of at least 4 hours if LP is done first, a gap of 1 hour if PET is done first.

Ideally, all patients will complete all baseline measures as dictated per protocol, however, if a patient cannot complete one of the measures, for example, tau PET (due to failure on the part of the Kreitchman PET Center, failure to successfully produce the ligand, an unforeseen scheduling conflict on the patient's part, etc.) we will not discontinue that patient from the protocol; instead, we will try to complete the procedure on another day. If that is not possible, write an exception or deviation, report to the IRB if needed, and continue the patient in the protocol.

PET, MRI and LP will take place at CUMC/NYSPI. It will be the responsibility of the NYU RC to obtain patient availability for MRI, both PETs, and LP (if applicable) at the end of the patient's screening visit and report to NYSPI staff within 24 hours. The NYU coordinator will email this availability (along with any forms such as PET Center Forms) to the NYPSI coordinator using patient ID, not name. Staff at NYSPI will schedule the patient for each respective procedure and will need the patient's availability as soon as possible in order to schedule each procedure as per the patient's request. The NYSPI coordinator will then communicate booked dates/times to the NYU team so they can communicate this information to their patient in timely manner. The MRI, PET scans, and LP should be scheduled by the NYSPI coordinator within one week of the NYU coordinators initial request.

Research Pharmacy Ordering Study Drug/Randomization: Procedures for All Sites

The New York State Psychiatric Institute pharmacy is the research pharmacy for the study. The randomization code was generated by the study statistician when the study began and this code is maintained by the research pharmacy with [name] who leads the Data Coordinating Center for the study. The research pharmacy updates the randomization table as participants enroll in the study and are dispensed study medication (valacyclovir or placebo) and sends the updated table to [name] on a monthly basis. Any discrepancies are resolved by the research pharmacy with [name].

For all Columbia/NYSPI, NYU and BAI patients: The NYSPI research pharmacy will manage study drug kit generation and send these out for the entire duration of each patient's protocol participation.

NYSPI pharmacy dispenses kits for NYSPI subjects on-site at clinic visits and when needed through shipping the kits to the home of the patient or caregiver. Each subject's first study drug kit will be dispensed by the NYSPI pharmacy to the study physician/research coordinator to be distributed at the baseline study visit. The pharmacy will send NYU/BAI kits to NYU/BAI RC's for later distribution to subjects by staff on site. NYSPI Pharmacy must include a receipt in every study drug shipment sent to sub sites, indicating what is included in each study drug shipment. These receipts are necessary for accession, filing and compliance purposes.

At least two weeks before the patient's scheduled Baseline visit, the Study Drug Order Form will be submitted to the NYSPI pharmacy by the NYSPI RC specifying kits for weeks 1-8 and 9-16. NYU and BAI coordinators will scan and send the study drug order form to NYSPI coordinators at least two weeks in advance, specifying

weeks 1-8 and 9-16. As a reminder, the study drug order form should not be submitted until a study physician confirms eligibility, the patient is contacted, and the baseline MRI/PET scans are scheduled.

Coordinators assign subject identification numbers for the protocol, ascending sequentially from 101 at NYSPI, from 1001 at NYU and from 2001 at BAI.

Randomization is not officially completed until the first bottle of study medication is handed to a patient at their baseline visit. Subject IDs will not be reassigned, even if a patient does not come back after baseline (once randomized, always randomized).

Study drug kits are broken down as follows:

(NYSPI) For weeks 1-12: 644 total capsules.

Week 1-2: 28 capsules x 2 bottles (2g per day, 1g morning (2 caps), 1g evening (2 caps)

Week 3-4: 42 capsules x 2 bottles (3g per day, 1.5g morning (3 caps), 1.5g evening (3 caps)

Week 5-8: 56 capsules x 4 bottles (4g per day, 2g morning (4 caps), 2g evening (4 caps)

Week 9-16: 56 capsules x 8 bottles (4g per day, 2g morning (4 caps), 2g evening (4 caps)

From then onward it's 56 capsules x 8 bottles (4g per day, 2g morning (4 caps), 2g evening (4 caps), unless clinically indicated by the study physician.

(NYU) For weeks 1-12: 644 total capsules.

Week 1-2: 28 capsules x 2 bottles (2g per day, 1g morning (2 caps), 1g evening (2 caps)

Week 3-4: 42 capsules x 2 bottles (3g per day, 1.5g morning (3 caps), 1.5g evening (3 caps)

Week 5-8: 56 capsules x 4 bottles (4g per day, 2g morning (4 caps), 2g evening (4 caps)

Week 9-12: 56 capsules x 4 bottles (4g per day, 2g morning (4 caps), 2g evening (4 caps)

Week 12-16: 56 capsules x 4 bottles (4g per day, 2g morning (4 caps), 2g evening (4 caps)

From then onward it's 56 capsules x 12 bottles (4g per day, 2g morning (4 caps), 2g evening (4 caps)), unless clinically indicated by the study physician.

It will be the responsibility of each RC to track when each replenishment is due (there is a log in each subject chart for this) and complete the study drug order form. Given that NYSPI pharmacy will be sending kits out to NYU and BAI RC's, it is the expectation that NYU and BAI coordinators scan and send a copy of the completed "Study Drug Kit Send Out Log" to coordinator(s) at NYSPI as a tracking and management tool. This will be done during the Baseline period. NYSPI, NYU and BAI kits will contain 4 months/16 weeks' worth of valacyclovir/placebo.

NYSPI, NYU and BAI RC's will complete the study drug order form at least two weeks prior to subject replenishment due date. NYU and BAI coordinators will scan and send completed study drug order form to the NYSPI coordinator for distribution to NYSPI Pharmacy team.

At all three sites, kits will be returned to coordinators at scheduled study visits so that compliance checks can be conducted in tandem with a check in with the patient regarding how they're feeling (update of AE and Con Med Logs should be completed at this time based on result of conversation with patient). Coordinators must call patients once a month to check in with the patient regarding medication compliance, and any AEs and Con Med changes.

Kits returned to NYU and BAI coordinators will be stored at respective pharmacy or other designated storage location, for later monitoring by the NYSPI team and eventual destruction at end of study.

NYSPI Pharmacy Team:

[name] ([contact]; Research Pharmacist) [name] ([contact]; Research Pharmacist) [name] ([contact]; Pharmacy Director)

Week 0 (Baseline) Visit: Procedures for NYSPI and NYU (BAI will follow this protocol with modification made per site facility standards) Details on MRI, PET scans, and LP procedures can be found in the specific Policy & Procedures Manual for each respective procedure located in the next section

Participation Standards: The team will re-iterate expectations, as it pertains to participating in the study, with both subjects and caregivers. In brief, if subjects/caregivers agree to participate, the expectation is that they will remain in the protocol for the entire 78-week duration.

Baseline measures will need to be completed over a span of a few days. Informants do not have to be present during all baseline study procedures, but the informant must drop off and pick up the subject (or make arrangements for this; research team staff can assist as well).

Description of NYU staff activity at NYSPI for all procedures is included in this manual as NYU staff may need to be present at each procedure if necessary, per subject request.

Prior to baseline, the RC will find out whether or not the subject has undergone any of the neuropsych testing that will be conducted per protocol. If so, any neuropsych test administered within the CUMC, NYU or BAI system 3 months or less prior to Baseline, can be used for the purposes of the protocol but this must first be checked with investigational staff for final approval. All data from historic neuropsych testing will be copied onto study specific CRFs, and entered into the VALAD database with the current, baseline date (not the date of original testing).

The coordinator will take vital signs and administer the ADAS-COG 11 and NACC Neuropsychological Battery. The coordinator will administer the UPSIT. Finally, the coordinator will complete the initial NACC packet (the GDS and 3-page demographics form). Qualified/certified staff at NYU and BAI will complete the aforementioned NACC measures, coordinators will complete all other measures as dictated per protocol.

The patient will then see the study physician, who will write a progress note and complete the MD NACC packet, the Concomitant Medications log, the CIBIC-Plus, and the CDR. The physician will also complete the ADCS-ADL with the informant. This informant interview can be done over the phone at a later time within the Baseline period, as well.

The coordinator will then draw blood for APOE genotyping (yellow top), which is to be stored at the Human Genetics Resources Core (HGRC). Both NYU and NYSPI subjects will have APOE drawn at NYSPI during Baseline, as will BAI subjects. BAI staff will store APOE on site for later send out to the HGRC. The RC will fill out the HGRC form as described in the blood draw policy section of this manual. The form and tubes will be checked by the RC who filled them out and the back-up RC. They will sign the corresponding accuracy log.

An extra serum tube (red top) will also be drawn for all subjects, processed, and stored in the -80 freezer on Pardes floor 4 (at NYSPI, BAI will store locally). Please see the Lab manual section for greater processing description.

As described in the consent forms, all clinically applicable information collected during the trial will be disclosed to patients and their caregivers, as well as interpretation of baseline MRI, 18F-Florbetapir amyloid PET radiological read, and results from CSF analysis.

After the baseline evaluation, the results of outcome measures specified in the hypotheses will not be disclosed. Apolipoprotein E genotyping results will not be disclosed nor will results from 18F-MK-6240 tau PET scan; tau PET imaging results are still in research development and there is no standardized method to make a clinical read and provide a report to the patient.

At both sites, the medication kit is dispensed when the study physician sees the patient and reviews the medication kit.

After all procedures for the day are completed, follow-up visits are scheduled. The RC must review the Checklist for the visit and ensure that all forms listed in it are completed on the checklist page before the patient leaves the clinic. The RC will double check that the study physician has completed all necessary forms, as well. After all verifications are complete, the patient and caregiver may be sent home.

A few important notes to keep in mind at Baseline:

- A. The ADCS-ADL must be done by the study physician who sees the patient (At BAI, neuropsych and rating scales are completed per site standard with trained staff and raters). It should be done at the end of the visit, i.e., after NACC and other forms are administered (specific forms will vary from visit to visit but ADCS-ADL should always be done at the end). The ADCS-ADL should be administered to the informant but when the informant is not sure about the answer to a question, it can be done with the patient as well. The study physician must fill it out completely based on the best information available, even if it seems to be spotty based on unclear patient and informant responses.
- B. We will use our own discretion in deciding whether subjects and caregivers should be compensated with Petty Cash, or through filling out a reimbursement form, which would result in a check being sent to the subject or caregiver's place of residence. Reimbursement forms require collection of social security number and W9 completion from the payee.
- C. The RC must do the maximum, not the minimum, and know every detail about their patient(s) to truly make this a successful study. There needs to be an ongoing conversation about patient concerns, not just facts of the study. The single most important thing will be establishing a decent rapport with the study patient and making sure they (as well as their caregivers) know that we're here to address their concerns and make participation in the study convenient for them. This will keep them coming back.

Weeks 2 & 4 Phone Call/Visit

- In-office or telephone call by study physician to assess subject study drug compliance and any patient history changes. This telephone call or in office visit should last approximately 10 minutes.
- Physician will write note and RC will complete medication compliance form.

Medication Compliance Calls: The RC will call the patients or caregivers **once a month** and medication compliance will be documented on a log upon query. These calls will occur throughout the subject's 78 weeks of protocol participation. During phone contacts, patients should be reminded that they will be followed by a physician here. Patients should know exactly what they'll be getting through participating in research.

The following compliand	ce script will be used when pla	cing these calls:
Hi Mr./Mrs.	. This is	calling from Columbia about the "Antiviral
		mily member is enrolled in. Do you have a few minutes

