- 6. Current or recent (past 6 months) alcohol or substance use disorder (DSM-5 criteria).
- 7. Current diagnosis of other major neurological disorders, including Parkinson's disease, multiple sclerosis, CNS infection, Huntington's disease, and amyotrophic lateral sclerosis.
- 8. Clinical stroke with residual neurological deficits. MRI findings of cerebrovascular disease (small infarcts, lacunes, periventricular disease) in the absence of clinical stroke with residual neurological deficits will not lead to exclusion.
- 9. Acute, severe, unstable medical illness. For cancer, patients with active illness or metastases in the last 12 months will be excluded, but past history of successfully treated cancer will not lead to exclusion.
- 10. Sitting blood pressure > 160/100 mm Hg Physician Evaluation
- 11. Renal failure as determined by an estimated Glomerular Filtration Rate (GFR) < 44 ml/min/1.73m².
- 12. Serum vitamin B12 levels below the normal range.
- 13. Patients with thrombotic thrombocytopenic purpura/hemolytic uremic syndrome will be excluded.
- 14. Use of benzodiazepines in lorazepam equivalent doses equal to or greater than 2 mg daily.
- 15. For patients consenting to lumbar puncture (40% of sample), this procedure will be conducted if there is no lower spinal malformation or other contraindication to lumbar puncture.
- 16. For MRI, metal implants and pacemaker, and claustrophobia such that the patient refuses MRI. In our experience, these exclusions occur in less than 5% of patients with mild AD. MRI is required for VALAD.
- 17. Radiation exposure in the prior 12 months that, together with 18F- Florbetapir and 18F-MK-6240 PET, will be above the FDA annual radiation exposure threshold. This will be determined through study staff (i.e. Principal Investigator, Study Physician) discussion with potential subjects at Screening, documenting inquiry about radiation history. If there is any history of additional radiation exposure in the past year; it will be reviewed with PET Center staff for their approval before proceeding. The combined radiation exposure from the maximum doses used for 18F- Florbetapir and 18F-MK-6240 is within the FDA limits for annual radiation exposure and the second scan in each patient will be done 18 months after the initial PET scan (for both radioligands).

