The study sample will be composed of outpatient participants who have been diagnosed with probable AD by NIA clinical diagnostic criteria and test positive for serum antibodies to HSV1 or HSV2. RC and MD will

complete the inclusion/exclusion criteria form. Patients who do not meet all inclusion/exclusion criteria will not enter the study and will be considered a screen fail and noted as such on the corresponding log.

Recruitment Logs: Logs to be kept at both study sites unless otherwise noted in description. The following logs will be used to track recruitment:

1) Patient Tracker: This log includes the tracking of active study patients, patients who have been scheduled for a screening visit, patients who are pending screening evaluation (but not yet scheduled), and patients who are pending/we are unable to contact. The last seen/contacted column should be updated every time the patient or caregiver is contacted.

NAME/	Referral	Study	Referral	Contact	Comm	Final
MRN	Source	MD/ RC	Date	info	ents	Status

2) DPO Referral Tracker (This log is NYSPI specific): This log tracks DPO subjects who were elucidated to be interested or eligible in their EPIC chart (and whose names were sent to [name] and [name] for pursuit by DPO providers) and their status in the referral process. This log also provides context as to why there was no referral (i.e. not interested or eligible after-all?) Context for this log comes from [name] as well as the patient's last DPO provider note.

Name	DPO	MRN	DOB	Age	Dx	Apt	Pertinent Hx	MMSE	MMSE Date	Eligible
						Date				

3) Screen Fails/Archived Subjects: This log tracks subjects who have come in for a screening visit but did not meet criteria to be enrolled in protocol.

NAME/	Referral	Study	Referral	Contact	Comm	Final
MRN	Source	MD/ RC	Date	info	ents	Status

4) Phone Screening Log: This log is primarily for the tracking of advertising respondents.

NAME/	Referral	Study	Referral	Contact	Comm	Final
MRN	Source	MD/ RC	Date	info	ents	Status

Study Visits

Prior to Screening Visit

The screening visit encompasses completion of the screening packet to determine eligibility as well as all consent procedures. Research staff at NYSPI must schedule 4-6 screening visits per week, distributed amongst study physicians as follows:

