It is a strict expectation that 24 hours prior to a VALAD screening visit the RC will review all records available in the EPIC chart, MDC chart, independent medical records sent in from external provider, etc. This is key to understanding who your patient is medically and personally.

RC Responsibilities during Study Visits:

From Screening until week 78, it is the expectation that the respective RC (ideally, the RC who conducted the phone screen with the patient) will be present in the exam room during all study visits, with patient and study MD, to preside over all activity and provide any relevant information, including self-reported measures such as the UPSIT. This will ensure that there are no gaps in knowledge or information shared throughout the duration of the patient's protocol participation.

The RC will always check all forms, both RC and MD, prior to the patient leaving the clinic, to ensure that all necessary measures were completed accurately. If another RC is present, they should cross check the forms. This should be done on the same date as the visit itself, no matter how late it gets.

Patients should take their regular medications prior to coming in for study visits. If they have medications that they take at lunchtime, they should bring them and take them at their regular dosing time when they are here. It is a good idea to take the patient's chart, and particularly their list of medications, along with the patient when there are procedures outside our clinic (such as MRI, PET, LP). Nurses or technicians at these other sites often wish to see the list of meds the patient is on and patients tend to lack reliability in reporting current medication administration.

Screening Visit: Procedures

NYU Capacity to Consent:

Per PI agreement: NYU subjects will sign all consent forms even if deemed as "not having capacity" (per NYU's standard, which is different from NYSPI's standard and includes MMSE and subjective consent quiz). There will not be notes in the NYU subject chart about lacking capacity. NYU will continue to abide by NYU's rules and standards NYU subjects lacking capacity will not undergo the LP.

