At screening, the patient meets with the study physician (or delegated staff at NYU and BAI) to be consented. The coordinator should be in the room to ensure their own understanding of the protocol and consent procedures and can supply physicians with necessary information. The physician will obtain signatures and sign the Patient and Caregiver Consent Forms, the PCS Cover Sheet and Form II, and the Consent Procedure Note with the patient and caregiver and review the inclusion/exclusion criteria. NYU and BAI will utilize their equivalent PCS Forms at the Screening visit. BAI patients only sign BAI consents. NYU subjects and caregivers will sign both NYU and NYSPI Patient and Caregiver consent forms to cover procedures performed at both NYU and NYSPI/CUMC facilities.

The RC then completes a "Patient Tracking Form," which outlines key information about subjects and caregivers. The RC then takes vitals (BP, pulse) and completes the MMSE with the patient. If blood pressure is high or out of range, the RC should repeat BP twice, 10 minutes apart each time. Any pressure above either 160 systolic or below 100 diastolic needs to be reported to an MD on site, for further instruction.

For MMSE, use the three words in the second or third array since patients who have been undergoing regular neurological follow up for memory disorders tend to be familiar with "apple, table, penny." This is necessary to ensure MMSE inclusion, barring circumstances where an MMSE has been documented in the previous month. The RC also completes the Informant FAQ if applicable per clinical standards, Metal Screening Questionnaire, and the Medical Records Release form with the patient and/or their caregiver.

It is recommended that measures used for determining eligibility be completed earlier within a visit; should a subject screen fail on key criteria early in the visit, there is no need to complete other study measures because this patient has already been found to be ineligible.

The patient then meets with the study physician again (or delegated staff at NYU and BAI) to discuss eligibility and review the inclusion/exclusion criteria again.

For patients who sign consent, an RC will draw blood for SMAC, CBC, and HSV. If patients are "difficult draws" at NYSPI, the NYSPI phlebotomist ([name]; [name]) will be contacted.

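### The screening blood-pressure instruction says *below* 100 diastolic where *above* 100 is needed to agree with exclusion criterion 10 (minor)

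*Protocol*

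**What the plan says.** Two places in the Protocol set blood-pressure thresholds for screening.

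- **Exclusion Criteria, item 10**, gives the eligibility limit: "Sitting blood pressure > 160/100 mm Hg Physician Evaluation". Both figures are upper limits. The item does not say whether a patient must exceed both or only one.
- **Screening Visit: Procedures** tells the coordinator what to do with the reading. First, "If blood pressure is high or out of range, the RC should repeat BP twice, 10 minutes apart each time". Then: "Any pressure above either 160 systolic or below 100 diastolic needs to be reported to an MD on site, for further instruction".

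Other sections bear on what happens next. Under Screening Eligibility, the coordinator and physician "complete the inclusion/exclusion criteria form. Patients who do not meet all inclusion/exclusion criteria will not enter the study". Later in the screening procedure the patient meets the physician again (or delegated staff at NYU and BAI) "to discuss eligibility and review the inclusion/exclusion criteria again". The same section adds: "A subject will not be considered eligible unless all inclusion/exclusion criteria are met", and "Inclusion/exclusion criteria checklist will be signed at screen or baseline by both research coordinator and study physician".

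**The concern.** The escalation instruction uses the two numbers of criterion 10 but turns the diastolic limit around. It stands directly after a sentence about raised or out-of-range pressure, so its purpose is evidently to bring high readings to a physician. With *below*, it cannot do that for the diastolic component. It flags nearly everyone with a normal diastolic pressure, and it is silent on a patient whose only abnormality is a diastolic pressure above 100.

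This is an operative threshold in a staff procedure, not background text. What is at stake is prompt physician review of isolated diastolic hypertension at screening and, on one reading of criterion 10, the enrolment of a patient who should have been excluded.

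**Working it through.** The plan gives no figure to reproduce, and no sample-size or power calculation depends on this point. The check is a comparison of rules. Let S be systolic and D diastolic pressure in mm Hg.

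**Rules compared**

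- Escalation as written (Screening Visit: Procedures): report if S > 160 or D < 100.
- Escalation as corrected: report if S > 160 or D > 100.
- Criterion 10, either-limit reading: exclude if S > 160 or D > 100.
- Criterion 10, both-limits reading: exclude if S > 160 and D > 100.

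**All possible readings**

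| Region | Reported as written | Reported as corrected | Excluded (either limit) | Excluded (both limits) |
|---|---|---|---|---|
| S > 160, D > 100 | yes | yes | yes | yes |
| S > 160, D ≤ 100 | yes | yes | yes | no |
| S ≤ 160, D < 100 | yes | no | no | no |
| S ≤ 160, D = 100 | no | no | no | no |
| S ≤ 160, D > 100 | **no** | yes | **yes** | no |

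**Examples under the rule as written**

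- 130/75: D = 75 < 100, so it is reported although neither limit is exceeded.
- 161/90 and 170/110: S > 160, so both are reported.
- 150/110: S = 150 is not above 160 and D = 110 is not below 100, so it is not reported.
- 160/101: S = 160 is not above 160 and D = 101 is not below 100, so it is not reported.

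**What follows**

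1. The rule as written never misses a reading with S > 160.
2. Under the either-limit reading, the only excluded readings it misses are those with S ≤ 160 and D > 100.
3. Under the both-limits reading, it misses no excluded reading and only over-reports.
4. The corrected rule misses no excluded reading under either interpretation. Under the either-limit reading it coincides with criterion 10 exactly.

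**Which wording was meant.** The phrase pairs *above either* with *or below*, which does not parse; *above* applied to both limits does. The figure of 100 is the diastolic limit in criterion 10. The preceding sentence is about pressure that is high or out of range. No other part of the Protocol or SAP gives a lower diastolic limit of 100 or explains the reversal.

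**The case against.** The best reply is that this is a slip of wording with almost no consequence. The sentence says when to call a physician; it does not decide eligibility. Criterion 10 does that, and it is stated correctly and itself refers to evaluation by a physician. Several controls work independently of the faulty sentence:

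- a high pressure is to be measured twice more;
- coordinator and physician complete the criteria form together;
- the criteria are reviewed again after the vital signs are taken;
- the coordinator "will be present in the exam room during all study visits, with patient and study MD" (RC Responsibilities during Study Visits);
- both sign the checklist;
- vital signs are taken again at week 0 (Table 1; Week 0 (Baseline) Visit).

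A patient at 150/110 would have to pass all of these unnoticed. Recruitment is closed and the SAP (section 2) describes 120 participants as already randomized. The effect on eligibility is also conditional on how criterion 10 is read, and only the study team can confirm the intended text. A lower limit of 100 on *systolic* pressure is a conceivable alternative.

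Most of this stands as a limit on the consequence. It does not correct the sentence. The escalation fault also does not depend on how criterion 10 is read: under any interpretation, the literal instruction fails to send 150/110 to a physician. At NYU and BAI the second review of criteria may be done by delegated staff, so the escalation has some value of its own there, although the study physician still co-signs the checklist. As for the alternative intent, the text says diastolic, and 100 is the diastolic figure in criterion 10, so *above 100 diastolic* is the repair that agrees with the rest of the Protocol.

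**Conclusion.** The instruction is wrong as written and should be corrected; the severity is low. It over-reports every reading with systolic at or below 160 and diastolic below 100, which is harmless. It fails to escalate readings with diastolic above 100 and systolic at or below 160. Whether any of those patients were ineligible depends on an assumption the Protocol does not settle, namely that exceeding either limit excludes.

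The documents contain no blood-pressure data, so the number of patients concerned cannot be estimated and may be zero. Given the other checks, wrongful enrolment through this sentence is unlikely. No future screening decision depends on it, and the endpoint, sample size, randomization and analysis are unaffected. That *above* was intended is an inference from the surrounding text, though a strong one.

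**What to change.** In Screening Visit: Procedures, change *below* to *above* before the diastolic limit, so that the coordinator reports any systolic pressure above 160 or any diastolic pressure above 100. This is a one-word edit.

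Two further steps are optional:

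- In exclusion criterion 10, add a phrase saying whether exceeding either limit is enough to exclude.
- If it is, list randomized participants with screening diastolic above 100 and systolic at or below 160. This is one filter on the screening vital signs of at most 120 people, and it would settle whether anyone was affected.
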